### Methods & Procedures:

We aim to compare stimulation parameters (frequency and amplitude, 1-ms pulses) using a monophasic waveform for different spinal segment sites to modulate BP. Sites for stimulation during a series of seated experiments will include 1) T 7/8; 2) T 9/10; 3) T11/12; and 4) L1/2, while beat-to-beat seated BP is continuously monitored and recorded in hypotensive individuals with SCI.

This study will take approximately 7-study visits, between 1-3 hours, per subject. Participants will be asked to arrive between 8:00 am and noon at the James J Peters VA Medical Center (JJP VAMC), after a normal breakfast and a good night sleep. The participants will be asked to not drink alcohol or caffeine 12 hours prior to their visit and there will be at least 3 days between study visits.

Approach: We will compare the electrode placement sites and amplitude during seated rest to modulate BP. We anticipate that BP responses will vary among the participants regarding the location of the electrode placement site and signal amplitude. Participants will visit the laboratory 8 times: visit 1): informed consent and medical intake to determine eligibility for enrollment in the study. Visits 2-8: amplitude (mA) mapping sessions at each electrode placement site (randomized), with continuous beat-to-beat BP monitoring at the finger arteriole and at 1-minute intervals at the brachial artery.

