Amplitude Parameter Mapping Visits 2-8: Before TSCS, electrodes will be placed on the vertebral midline at the spinous process (T7/8, T9/10, T11/12, L1/2), and the active site will be randomized. Each visit, we will complete one electrode placement site. Amplitude ramping will start at 10mA, with 10mA increments (pulse width, 1ms, frequency 30 Hz as shown (13)). Continuous real-time BP and heart rate will be measured for 5-minutes, before, during and after stimulation. During ramping, amplitude will stop increasing when SBP reaches optimal SBP between 110-120 mmHg (100-120 mmHg females) or reaches 100 mA with no SBP response (see below TSCS decision Tree). Amplitude will be decreased in 10 mA decrements in stimulation. BP will be continuously recorded during the rest period. Bilateral muscle activation (rectus femoris, medial hamstring, and gastrocnemius) will be monitored during all experiments to determine if skeletal muscle contractions are contributing to increases in BP. Additionally, signs and symptoms of autonomic dysreflexia will be monitored during TSCS testing in visits 3-6 by a questionnaire (**Appendix**). After every incremental increase of amplitude, investigator will ask participant if he/she is experiencing any symptoms. Maximum ramping amplitude will be 100 mA and testing will be halted if participant experiences any discomfort during testing. Based on preliminary work, regulation of neuromodulation of BP will occur at stimulation levels less than 100mA.

Participants will be notified by investigator if any of the findings from this study will affect the participants' health or welfare.

- Cardiovascular Assessments: While the subject is seated 3 ECG electrodes will be affixed to the chest and abdomen for continuous monitoring of HR and respiration rate (RR). Brachial BP will be monitored at 1 minute intervals using a standard adult BP cuff placed at the right upper arm, and beat-to-beat finger arteriolar BP will be continuously monitored from the right

middle finger throughout testing. Mean arterial pressure (mmHg) will be calculated from brachial BP using the formula: [systolic BP + (2\* diastolic BP)]/3. Beat-to-beat HR, RR and BP data will be viewed in real-time and stored for subsequent analysis using customized programs created with LabView graphical software.

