Targeted Transcutaneous
Stimulation to Restore Autonomic
Cardiovascular Health in Veterans
with Spinal Cord Injury

NCT05180227

August 18, 2025

Statistical analysis plan:

The primary outcome variable will be systolic blood pressure. Data will be analyzed with a mixed-modeling approach to determine which stimulation parameters consistently yield increases in systolic blood pressure. Participant will be modeled as a random effect and stimulation characteristics as fixed effects including: cathodal stimulation site (T7/8, T9/10, T11/12, and L1/2); stimulation frequency (30, 60, 120 Hz); waveform (monophasic, biphasic, asymmetric biphasic); pulse width (40 - 1000 μ s); carrier frequency (0, 10kHz); and stimulation current (0–120mA). To quantify the effect size of each participant's optimal tSCS parameters, each participant's blood pressure response will be compared to baseline blood pressure to calculate Cohen's d and confidence intervals. All analyses will be performed using R software. The lme4 package will be used to perform the mixed-models analyses for the ratio-scale data. The ordinal package in R will be used to analyze the Likert-scale-type data. The 95% level of confidence will be used. We used the R software simr package for multi-level models for power calculations with fixed effects variables of waveform and electrode site. Given the number of repeated measurements of SBP in each participant, we anticipate having *95% power to detect <2-mm-Hg mean differences at the 95% level of confidence.

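### The SAP models and powers on waveform, and also models pulse width and carrier, but the supplied protocol schedules no session that varies any of the three; separately, the stated 95% power for site cannot be checked

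*SAP*

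**What the plan says.** **SAP.** The primary outcome is SBP, analysed by a mixed model with participant as a random effect and six stimulation characteristics as fixed effects. These are site (four levels), pulse width (40 to 1000 microseconds), "stimulation frequency (30, 60, 120 Hz); waveform (monophasic, biphasic, asymmetric biphasic") and "carrier frequency (0, 10kHz); and stimulation current (0–120mA"). The power basis is "We used the R software simr package for multi-level models for power calculations with fixed effects variables of waveform and electrode site". The result is stated as "Given the number of repeated measurements of SBP in each participant, we anticipate having *95% power to detect <2-mm-Hg mean differences".

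**Protocol, Methods & Procedures.** The aim is "We aim to compare stimulation parameters (frequency and amplitude, 1-ms pulses) using a monophasic waveform for different spinal segment sites to modulate BP". The approach is "We will compare the electrode placement sites and amplitude during seated rest to modulate BP", and visits 2-8 are described as "amplitude (mA) mapping sessions at each electrode placement site (randomized"). The mapping paragraph adds "Amplitude ramping will start at 10mA, with 10mA increments (pulse width, 1ms, frequency 30 Hz as shown (13")) and says that each visit completes one site. No biphasic waveform and no carrier appears anywhere in the protocol.

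**The concern.** The primary analysis is meant to show which stimulation parameters raise SBP. A factor observed at one level has no effect to estimate. On the protocol's schedule, three of the SAP's six factors are in that position, and one of them, waveform, is half the basis of the only power statement. Current, which is named in Hypothesis 1 alongside site, was not among the simulated factors.

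If this stays open, the primary model will have to be cut down after data collection, and the stated power will refer partly to a comparison that the documented design does not contain.

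**Working it through.** **1. Parameters side by side**

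| Parameter | SAP | Protocol |
|---|---|---|
| Waveform | 3 types | monophasic only |
| Pulse width | 40-1000 microseconds | 1 ms only |
| Carrier | 0, 10 kHz | not mentioned |
| Frequency | 30, 60, 120 Hz | 30 Hz for the ramp; the aim and the stimulation paragraph speak of comparing frequencies, but 30 Hz is the only value given for this study |
| Current | 0-120 mA | maximum 100 mA (mapping paragraph and decision tree) |
| Site | 4 | the same 4 |
| Visits | not stated | about 7, and also 8 (Methods & Procedures); 9 (Study Compensation) |

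**2. What can be estimated if the protocol governs**

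Taking current and pulse width as linear terms (an assumption), the SAP main-effects model has these columns: intercept 1 + site 3 + frequency 2 + waveform 2 + pulse width 1 + carrier 1 + current 1 = 11, of which 10 are effects.

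- Waveform (2), pulse width (1) and carrier (1) do not vary, so 4 of the 10 effects cannot be estimated whatever happens with frequency.
- If 30 Hz is the only frequency, its 2 columns are also constant. A matrix built on four sites with the current ramp has rank 5 of 11: intercept, three site terms and current. Six of the 10 effects cannot be estimated.
- A model with site and current alone has full rank, 5 of 5. Removing constant columns does not bias it.

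With one waveform observed, power for a waveform contrast is undefined.

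**3. The stated 95%**

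It cannot be reproduced under either document. The SAP gives no contrast, participant SD, visit SD, reading SD or number of readings. The following is an illustration only.

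From the documents: 12 participants, a 2 mmHg difference, and the 5% level implied by 95% confidence. Assumed: a two-sided test, one visit per site, independent readings, and all SDs and reading counts.

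SE of a two-site difference = sqrt[2 × (visit SD² + reading SD²/m) / 12], where m is readings per visit. Power comes from the noncentral t with (12 − 1) × (4 − 1) = 33 df.

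| Visit SD | Reading SD | m | SE | 2/SE | Power |
|---|---|---|---|---|---|
| 0 | 5 | 20 | 0.456 | 4.38 | 99% |
| 0 | 10 | 60 | 0.527 | 3.79 | 96% |
| 1 | 5 | 60 | 0.486 | 4.12 | 98% |
| 2 | 5 | 60 | 0.858 | 2.33 | 62% |

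For example, at visit SD 2: 25/60 = 0.417; 2 × (4 + 0.417)/12 = 0.736; the square root is 0.858.

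Extra readings shrink only the second term in the bracket. With unlimited readings and one visit per site, 95% power for 2 mmHg needs a visit SD of at most about 1.32 mmHg. With two visits per site, the last row becomes SE 0.607 and power 89%.

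**The case against.** **The SAP may describe a later design.** It is dated August 18, 2025, and the supplied protocol text carries no date. If the SAP reflects what is delivered, the waveform, pulse-width and carrier effects may be estimable and the simulation meaningful. This stands, and it is why the estimability result is conditional. The disagreement itself is not conditional: in that case the protocol lacks the sessions.

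**There may be room in the schedule.** Visits 2-8 are seven visits for four sites at one site each, so three have no stated content. A stimulated tilt (Abstract; Transcutaneous spinal cord stimulation) may use some, and the visit total itself is unsettled. The Review of Literature also says that pulse width needs to be understood. All true, but the visits are labelled amplitude mapping, none is assigned another waveform, pulse width or carrier, and the background remark schedules nothing.

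**The consequences are limited.** Site and current, the factors in Hypothesis 1, remain estimable. The participant-level Cohen's d does not depend on a waveform term, and the recruitment target of 12 is not derived from the power statement. This stands and holds the severity down.

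**The power figures rest on invented SDs.** Also true. A reader might infer that the 95% is wrong or overstated for site. The documents do not support that: it is reached under some inputs and missed under others, and the 1.32 mmHg limit applies only to one visit per site.

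**Conclusion.** Wrong as written, and should be fixed: the power statement rests partly on a waveform contrast that the documented design does not contain.

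- **If the protocol governs,** waveform, pulse width and carrier effects cannot be estimated: 4 of 10 effects, or 6 of 10 (rank 5 of 11) if 30 Hz is the sole frequency, given linear terms for current and pulse width. Waveform power is undefined.
- **If the SAP governs,** the protocol does not schedule the settings that it needs.
- **Whichever governs,** the 95% for site is unverifiable, and repeated readings alone do not guarantee it.

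Two further inferences go too far. One is that the primary analysis fails altogether; site and current survive, without bias. The other is that frequency is certainly inestimable; the protocol speaks both of a single 30 Hz setting and of comparing frequencies, so that is unresolved.

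**What to change.** 1. Reconcile the protocol and SAP on waveform, pulse width, carrier, frequency, current range and visit schedule. This review takes no view on which settings are right.
2. Restrict the primary model to the parameters actually delivered. If the SAP's extra parameters are intended, state in the protocol the visits and random order in which they are tested.
3. Rerun and restate the power for the factors actually varied. Name the contrast, and report the participant SD, the visit-within-participant SD, the reading SD and the readings per visit. The visit term is needed because each visit tests one site.

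The cost is SAP wording, one rerun of the simulation and a short protocol clarification. A fuller protocol amendment is needed only if the extra parameters are to be delivered.
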